5.1.1.1 Parameter of Interest

The parameter of interest is the percent of subjects with stricture formation.

5.1.2 *Primary Efficacy Objective 2*

To record incidence of recurrence of BE with HGD through 12 months following TECR with ECM placement. Incidence of disease recurrence will be confirmed endoscopically with pathology reviewed biopsies at 2 weeks, Month 1, Month 3, Month 6, Month 9, and Month 12 post procedure, and the proportion of subjects with and without disease recurrence at the trial endpoints will be compared to historical data.

5.1.2.1 Parameter of Interest

The parameter of interest is the percent of subjects with recurrence of BE.

5.2 Primary Safety Objectives

Safety of TECR with ECM placement will be assessed via two primary safety objectives that will assess the acute safety of the devices and implant procedure, and long-term safety of the treatment technique. Both primary objectives will be considered to demonstrate overall safety of TECR with ECM placement.

5.2.1. *Primary Safety Objective 1*

To demonstrate the acute safety of TECR with ECM placement for treatment of BE with HGD by evaluating all serious adverse events occurring in the first 2 weeks post procedure.

5.2.1.1 Parameter of Interest

The parameter of interest is the proportion of subjects with any serious, acute (within 2 weeks post-procedure) adverse events.

5.2.2. Primary Safety Objective 2

To demonstrate the long-term safety of TECR with ECM placement for treatment of BE with HGD by evaluating all study related adverse events occurring more than 2 weeks post procedure through the study endpoint at 12 months post procedure.

5.2.2.1 Parameter of Interest

The parameter of interest is the proportion of subjects with any serious, long-term (after 2 weeks post-procedure) adverse events.

The endpoint is any serious, long-term (after 2 weeks post-procedure) adverse event attributable to the TECR with ECM placement procedure. All adverse events will be classified according to severity and relatedness, and will be reported to the IRB and/or FDA (as necessary) based on 3.4.12.

5.3 Secondary Objectives

The following secondary objectives will be recorded.

5.3.1 Secondary Objective 1

To record the incidence of stent migration at 2 weeks post procedure. Stent migration will be determined endoscopically, and defined as any movement from initial deployment location greater than 1cm.

5.3.2 Secondary Objective 2

To record the number of subsequent follow up treatment interventions required post-procedure through the trial endpoint at 12 months.

5.3.3 Secondary Objective 3

To record the incidence and nature of poor stent integrity during placement and removal (broken wires, fracturing etc.)

5.4 Size and Duration of Trial

Ten (N=10) subjects will be enrolled in this study. Follow-up on each subject will be 12 months, except in the case of early death, losses to follow-up, or other censoring events.

5.5 Possible Future Analysis

In the event this study is expanded to enroll a greater number of individuals and/or extended to include those with T1a esophageal adenocarcinoma, additional thought has been given to potential statistical analysis for assessing overall efficacy and safety outcomes. Below is a description of potential future statistical analysis based off of an enrollment of 30 or more individuals.

5.5.1 Future General Statistical Methods

All patients that undergo TECR with ECM placement for treatment of BE with HGD and/or superficial (T1a) EAC during the study period will be included in the analysis. There are two primary efficacy endpoints: the proportion of patients with stricture formation requiring dilatation ($\geq 30\%$ reduction in esophageal luminal diameter) and the proportion of recurrence of BE with HGD and/or superficial (T1a) EAC during the 12 months post initial procedure. The primary safety endpoints will be the proportion of patients experiencing either a serious system or procedural adverse event during the 2 week post initial procedure period or any study related adverse event occurring during the 12 months post initial procedure period.

Data analysis will begin with assessment of the normality of the data using the Shapiro-Wilk test and a frequency histogram with normal overlay. Normally distributed data will be reported as means and standard deviations; non-normally distributed data as median (interquartile range). Categorical data will be reported as counts and percentages. Descriptive statistics will be presented for demographic, comorbid, clinical, laboratory and procedural data. One-way repeated-measures analysis of variance with the Tukey post-hoc test will be used to compare baseline and follow-up measures for continuous variables. The non-parametric Friedman test will be used when the dependent variable being measured is ordinal or the data violates the assumption of normality. The rates of all types of adverse events by event type will be summarized using counts, percentages, and graphical displays and reported at their designated follow-up time. Serious system and procedural related adverse events will also be combined and similarly reported. Adverse event and survival curves will be calculated from the date of the initial procedure according to the Kaplan-Meier method. The log-rank test will be used to compare the Kaplan-Meier curves. For event-free and BE-free survival, patients who failed one or both events will be censored at the time of the first failure. Univariate and multivariate Cox proportional hazards regression will be used to identify predictors of adverse events and to determine the hazard rate with a 95% confidence interval. Diagnostic tests of the assumptions of the Cox model will be performed using Schoenfeld residuals. Statistical tests will be two-sided and a value of $P < .05$ will be considered statistically significant. Statistical analyses will be performed using IBM-SPSS Statistics, version 20.0 (IBM-SPSS Inc., Armonk, NY). Graphs and charts will be done using MedCalc, version 13.1.0 (MedCalc Statistical Software bvba, Ostend, Belgium) and Microsoft Excel 2010.

5.5.2 Subgroup Analysis

One subgroup analysis will be performed. The cohort will be subdivided into two groups based on endoscopic biopsy at baseline. Group 1 will consist of patients with High Grade Dysplasia and Group 2 will consist of patients with T1a EAC. Descriptive statistics will be presented for

demographic, comorbid, clinical, laboratory and procedural data. A two-sample t-test will be used to compare continuous variables between groups. A chi-square test or Fisher's exact test will be used to compare categorical variables. A two-way repeated-measures analysis of variance with the Tukey post-hoc test will be used to compare baseline and follow-up measures for continuous variables.

5.5.3 Questionnaire Data Analysis

Descriptive statistics will be provided for items that comprise the Dysphagia Severity Questionnaire, Gastroesophageal Reflux Disease-Health Related Quality of Life Questionnaire (GERD-HRQL), and Short Form-36 Health Survey (SF-26). For all patients, changes in scores from baseline to 12 months post initial procedure will be compared using the paired t-test or Wilcoxon signed-rank test. Separately, changes in scores between patients with High Grade Dysplasia versus T1a EAC will be first compared within each group then between groups using the two-sample t-test or Mann Whitney U test. Internal consistency of the scales, both at baseline and 12-months post initial procedure, will be measured by Cronbach's alpha.

5.5.4 Primary Efficacy Objectives Analysis

All patients that undergo TECR with ECM placement for treatment of BE with HGD and/or superficial (T1a) EAC and who have stent removal at Week 2 with at least one valid follow-up EGD biopsy collection will be included in the primary efficacy analyses. Counts and percentages of patients that have stricture formation requiring dilation will be summarized for each follow-up time and totaled at the study endpoint. At 12-months post initial procedure, the proportions of patients who did and did not have stricture formation requiring dilation will be compared using the chi-square test. Time-to-events will be analyzed by the Kaplan-Meier method and Cox regression. Univariate and multivariate logistic regression will be performed to identify which variables were predictive of stricture formation requiring dilation. Demographic, comorbid, clinical, laboratory and procedural data will be included as covariates in the logistic regression models. Analysis using historical data for stricture incidence is based off of a 41% observation rate (19).

Similarly, counts and percentages of patients with recurrence of BE by 12-months post initial procedure will be reported. At 12-months post initial procedure, the proportions of patients with versus without recurrence of BE will be compared. Time-to-events will be analyzed by the Kaplan-Meier method and Cox regression. Univariate and multivariate logistic regression will be performed to identify which variables were predictive of recurrence of BE. Demographic, comorbid, clinical, laboratory and procedural data will be included as covariates in the logistic regression models.

5.5.5 Primary Safety Objectives Analysis

The analysis will begin with the counts and related percentages of all adverse events by event type (serious system and procedure-related) occurring during the first 2 weeks post initial procedure and later, of all serious system related adverse events occurring more than 2 weeks

post initial procedure through 12 months post initial procedure. Two outcome variables, serious system adverse events and procedure-related adverse events, occurring during the first 2 weeks post initial procedure, will be combined to provide a sufficient number of events for analysis. Time-to-events will be analyzed by the Kaplan-Meier method and Cox regression. Univariate and multivariate logistic regression will be performed to identify which variables were predictive of adverse events during the first 2 weeks post initial procedure and later, of all serious adverse events occurring more than 2 weeks post initial procedure through 12 months post initial procedure. Demographic, comorbid, clinical, laboratory and procedural data will be included as covariates in the logistic regression models.

Statistical analysis submitted by [name] M.S.

5.6 Ancillary Analyses

The following ancillary or supportive analyses will also be performed with data collected in this trial.

- 1) Summarize procedure-related complications and observations
- 2) Summarize the rates of all-cause adverse events

6. RISK ANALYSIS

6.1 Benefits

TECR with ECM placement is a novel endoscopic approach for the treatment of BE with HGD. Direct benefits regarding this procedure would include the following: organ (esophagus) preservation, no external surgical incisions required, less pain, short hospital stay and sooner return of the patient to usual activities compared to alternative surgical treatment options such as esophagectomy.

6.2 Risks

It is anticipated that subjects participating in the study will be exposed to operative and post-operative risks similar to related surgical procedures of the esophagus for the treatment of BE with HGD. Additional risk may include breach of confidentiality as a result of participating in this research study.

Stent removal may pose additional risks that are not fully known at this time. Removal of a fully covered metal stent is not an FDA accepted use of this device.

Potential complications of TECR with ECM placement include, but are not limited to, the following:

- Pharyngolaryngeal pain, temporary abdominal or esophageal pain, post-operative dysphagia due to edema or esophageal stricture, narrowing of the esophagus, nausea, vomiting, musculoskeletal pain (e.g. left shoulder pain), oral or dental injury, and heartburn, are usually mild in severity and may occur in greater than 25% of people.
- Laceration or tear of esophagus, post-operative bleeding, and stent migration are usually moderate to severe in severity and may occur in 1-10% of people.
- This procedure is rarely (less than 1%) associated with severe complications such as pneumothorax, pneumomediastinum, pleural effusion, nerve damage, esophageal perforation, infection in the center compartment of the chest, and arrhythmia. Patients may require conversion to open surgery.
- Failed endoscopic procedure (recurrent disease or narrowing of the esophagus which proves difficult to manage).
- Food bolus impaction is possible due to noncompliance with post-op dietary plan while the stent is in place.
- Allergic reaction to ECM (porcine material). The risks of prolonged contact with porcine derived material such as ECM are not fully known however it is possible that an individual could become sensitized to pork products as a result of this procedure.

Potential complications and complication rates of stent removal post ECM placement are not fully known and may include, but are not limited to:

- Bleeding – bleeding is common however generally subclinical and not severe
- Abrasion – superficial esophageal abrasions are usually visible however they are not typically severe
- Laceration to the esophagus – laceration is rarely observed with stent removal however can pose additional bleeding risk, and pain.
- Perforation of the esophagus

Patients who undergo this procedure will be closely monitored by the investigators on an ongoing basis throughout the study. If an adverse event listed above occurs, the investigator will immediately employ proper management to correct and/or minimize further complications.

Furthermore, EGD, and the study procedure are performed under general anesthesia which poses a potential risk of genetic mutations and birth defects. BaSW and fluoroscopic placement of the esophageal stent expose a subject to small amounts of radiation. The reproductive risks of this procedure for women (and on embryos or fetuses if they become pregnant) are not fully known and are unforeseeable. If subjects are female and of child-bearing potential, subjects will undergo a pregnancy test prior to their participation in the study procedures. Tests have not been done to determine the risk of this procedure to pregnant women. To avoid risks to the fetus, it is important that subjects not be pregnant during this study. It is also advised that subjects not become pregnant for at least six months after the study procedure, as it may impact the outcome of the study procedure. Avoiding sexual activity is the only certain method to prevent pregnancy. However, if subjects choose to be sexually active, they should use an appropriate “double barrier” method of birth control (such as female use of a diaphragm, intrauterine device (IUD),

or contraceptive sponge, in addition to male use of a condom) or the female should be using prescribed “birth control” pills, injections or implants (3.2.1). If subjects choose to be sexually active during this study, pregnancy could still result even with the use of these birth control methods. If subjects have questions, they are encouraged to speak with either the study investigator or their personal physician.

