3.2.2 Exclusion Criteria

If any of the following criteria are met, subjects are not eligible for this study:

1. Have lesions into or deeper than mucosal layer (superficial (T1a) Esophageal adenocarcinoma).
 - a. Those requiring endoscopic submucosal dissection (ESD) are not eligible for this study
2. Have presence of lymphovascular invasion.
3. Require resection length longer than 10 cm.
4. Have any lymph node or other metastatic involvement based on EUS and FDG-PET/CT.
5. Have history of any kind of previous esophageal surgery (i.e. anti-reflux surgery).
6. Are pregnant or planning to become pregnant.
7. Have coagulation disorders.
8. Have a known hypersensitivity to porcine-based materials.
9. Have an uncontrolled comorbid medical condition that would adversely affect participation in the trial.
10. Has a clinically significant psychological illness that in the physician's opinion would prohibit the subject's ability to meet the protocol requirements.
11. Are unable or unwilling to provide informed consent and/or fulfill the protocol follow-up requirements.

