3.3 Visit Windows

The following are allowable date ranges for each follow-up period:

Time Point	Date Range
Screening Evaluation and Baseline	Chart Review and Date of Informed Consent up to Day 0
Clearance tests (optional): ECG, PFT, CXR	Within 30 days prior to Day 0
TECR with ECM Placement (Day 0)	Within 60 days of the Screening Evaluation
Day 1	24 hours following Day 0 \pm 6 hours
Week 2	14 days following Day 0 \pm 4 days
Month 1	30 days following Day 0 \pm 7 days
Month 3	90 days following Day 0 \pm 15 days
Month 6	180 days following Day 0 \pm 30 days
Month 9	270 days following Day 0 \pm 30 days
Month 12	360 days following Day 0 \pm 30 days

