4. DATA COLLECTION

The following table lists the various intervals at which data is to be collected:

Interval	Data To Be Collected	Time of Collection
Screening/Baseline	ICF Demographics Medical history Prior medications Physical exam Pregnancy test (females) Results from the following: PET/CT Scan EUS BaSW	Prior to Treatment

	EGD with Biopsy EMR Blood Work Chest X-ray (if required) ECG (if required) PFT (if required) Questionnaires	
Treatment	TECR with ECM Placement Documented Dietary Consult	Day 0
Initial Follow-Up	BaSW	Day 1
Stent Removal	Stent Removal EGD with Biopsy EGD Photos Dilation of Stricture if present Questionnaires Vitals	Week 2
Follow-Up	EGD with Biopsy EGD Photos (months 1,3,12) Dilation of Stricture if present Questionnaires Barium Swallow x-ray test Vitals	Month 1, 3, 6, 9, 12
Anytime	Concomitant medications Adverse Event Follow-Up Adverse Event Protocol Deviation/Violation Death Termination	At Time of Occurrence, or When Notified of Event

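### As readable, the plan lets a pregnancy test up to 60 days old clear a subject for the procedure; a Day 0 test is allowed but not required

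*Combined protocol and SAP*

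**What the plan says.** All references are to the combined protocol and SAP.

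- **Exclusion.** Exclusion 6 in 3.2.2 removes women who "Are pregnant or planning to become pregnant". Section 3.4.10 makes the absence of any exclusion factor a condition for going on to TECR with ECM placement.
- **Test.** Section 6.2: "If subjects are female and of child-bearing potential, subjects will undergo a pregnancy test prior to their participation in the study procedures". It gives no maximum age for the result.
- **Timing of the test.** In the Section 4 table, the entry that begins "Pregnancy test (females" is in the Screening/Baseline row, to be collected before treatment. The Treatment row (Day 0) lists only the procedure and a documented dietary consult. No later row lists a pregnancy test.
- **Windows.** Section 3.3 runs the screening and baseline period from "Chart Review and Date of Informed Consent up to Day 0" and lets the procedure fall "Within 60 days of the Screening Evaluation". The optional ECG, PFT and chest x-ray have a limit of their own: "Within 30 days prior to Day 0".
- **Hazard.** Section 6.2 says that general anesthesia carries a possible risk of birth defects, and that barium swallows and fluoroscopic stent placement involve a small radiation dose.

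**The concern.** The pregnancy test is the only objective check on exclusion 6 that the readable text describes. Pregnancy status can change at any time after a negative result, so the test supports eligibility only if it is done close to the procedure. As written, it may be done at the Screening Evaluation and not again before Day 0. A woman who conceived in between could have general anesthesia and fluoroscopy with a fully compliant file, although the protocol meant to exclude her and itself names the fetal hazard.

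What is at stake is the safety of a subject and a fetus, and whether eligibility on Day 0 can be documented. No endpoint, analysis or efficacy estimate depends on it.

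**Working it through.** The plan gives no figure for the age of the test, so there is none to reproduce. The check is date arithmetic on the windows.

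**Inputs**
- Latest Day 0: 60 days after the Screening Evaluation (3.3).
- Earliest test date: taken as the Screening Evaluation, because Section 4 assigns the test to that interval. This is an assumption; the text does not name the day.
- Latest test date: Day 0, since the baseline period in 3.3 runs up to that day.
- Comparison limit: 30 days before Day 0 for the optional clearance tests (3.3).
- Sample size: 10 (5.4).

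**Age of the test on Day 0** = (Day 0) − (test date)
- Oldest compliant result: 60 − 0 = 60 days.
- Newest compliant result: 60 − 60 = 0 days.
- Compliant range: 0 to 60 days. The upper end is 60 − 30 = 30 days beyond the limit on the optional clearance tests.
- With a required Day 0 test: 0 days.

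**What each rule needs and what the test gives**
- Exclusion 6 and 3.4.10 together need the subject not to be pregnant when the procedure starts.
- A negative test at the Screening Evaluation speaks only to that date. It says nothing about conception in the following 60 days at most.
- The Day 0 row of Section 4 adds nothing to close that interval.

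**Subjects affected.** The plan does not give the number of women of child-bearing potential. It lies between 0 and 10. Eligibility runs from age 18 to 80 (3.2.1), so such women can enroll. At one added test each, the fix means 0 to 10 extra tests in the whole study.

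**The case against.** **Table 1 may already settle it.** Section 3.1 says that Table 1 sets out the procedures at each visit, and Table 1 is not readable here. A Day 0 test could be listed there, or in the case report forms. This stands as the main limit on the point. The Section 4 table can be read, however, and its Day 0 row has no such test.

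**Sixty days is a ceiling, and a Day 0 test complies.** True. The point is that the plan also accepts the 60-day-old result.

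**Exclusion 6 applies whatever the test date.** Also true, and a woman planning pregnancy is excluded. Subjects count as enrolled from consent (3.4.4), so the advice in 6.2 on contraception during the study can be read as covering the wait for the procedure. That lowers the chance of a pregnancy in the interval. But 6.2 itself concedes that pregnancy may occur despite contraception, and an exclusion rule without a current test relies on the subject knowing her status.

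**The 30-day comparison is weak.** This has force. Sections 3.4.9.9 to 3.4.9.11 count the 30 days from the evaluation, not from Day 0, and the blood work in 3.4.9.8 has exclusion thresholds but no recency limit of its own. The pregnancy test is not singled out. The comparison shows only that the plan sets recency limits for some tests; the point does not depend on it.

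**A stronger reading that does not hold.** A reader might infer that protection lapses before the late x-rays, because the only numbered avoidance period in 6.2 is a minimum of six months. The Month 9 visit is "270 days following Day 0" and the Month 12 visit is "360 days following Day 0", each with a 30-day allowance. Taking six months as 180 days, the earliest Month 9 visit is at 270 − 30 = Day 240, which is 60 days later, and the latest Month 12 visit is at 360 + 30 = Day 390, which is 210 days later. Those gaps are correct as arithmetic but do not measure a lapse. Just before the six-month advice, 6.2 asks for the sake of the fetus that no subject be pregnant while the study lasts, and 5.4 defines follow-up as 12 months. The six-month sentence is an added minimum, and its stated reason is the result of the procedure, not fetal exposure. Naming Month 12 there would only be a preference of wording.

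**Conclusion.** The point holds for the timing of the pregnancy test and for nothing wider. On the readable text, a negative result up to 60 days old clears a subject for a procedure that a pregnant woman must not have, and no test on the day is required. This goes beyond missing detail, because the stated timing allows an out-of-date result to satisfy an exclusion criterion.

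Its practical size is small: one center, 10 subjects, an unstated and probably small number of women of child-bearing potential, and no effect on any efficacy result. It is a cheap improvement in patient safety.

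The conclusion rests on two assumptions: that the test may be done as early as the Screening Evaluation, and that Table 1 and the other unreadable attachments do not already require a Day 0 test. If they do, only the Section 4 table needs to be brought into line.

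**What to change.** First check Table 1 and the case report forms. If neither requires a Day 0 test:

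- In 3.3, add a line requiring a negative pregnancy test on Day 0, before anesthesia, for women of child-bearing potential.
- In Section 4, add the same item to the Treatment row.

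Either move the existing test to Day 0 or keep the screening test and repeat it. Repeating keeps the early screen, so that a pregnant woman is identified before EUS and PET/CT where possible; moving it adds no test at all.

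The cost is two one-line edits and at most one extra simple test per woman of child-bearing potential. The Day 0 result has to be available before anesthesia starts. No change to sample size, endpoints or analysis is needed.
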